7.5. Outcomes (include DAG diagrams to show relationships between exposure and outcomes)

Table 5: Outcomes and associated confounders and covariates

Exposure of interest	Outcome	Confounders/Covariates	Rationale
Combined	Pulmonary outcomes	Smoking	Affects lung function
hormonal contraception (CHC)	 Annual pulmonary exacerbation rate (PEx) (defined as episodes requiring intravenous 	Insurance status (reflection of SES)	Will be used as socioeconomic indicator. Less access to meds may mean less
&	antibiotic use at home or in		compliance
Progestin-only	hospital)Absolute change in FEV1 (in	Age	Lung function worsens as one ages
contraception	liters) Prevalence of micro-organism (defined as 1 or greater sputum	Education (reflection of SES)	Affects contraceptive knowledge decision making
	culture within a 12-month period)P. aeruginosa	ВМІ	Associated with better or worse health status in general

Exposure of interest	Outcome	Confounders/Covariates	Rationale
	 MDR P. aeruginosa Staph aureus 	Exercise	May reduce pulmonary exacerbation rates
	MSSA MRSA	CF genotype class	Associated with severity of disease
	Secondary infections: • Burkholderia cepacia	CFTR modulator treatment	Likely preserves pulmonary decline
	 Burkholderia cenocepacia Mycobacterial species –includes M. tuberculosis and NTM species 	Comorbidity with CFRD (defined as requiring chronic insulin therapy) (11)	Associated with worse disease (reduced immunity)
		Length of hormonal contraceptive use (person-year of exposure)	
	Venous/arterial thromboembolism (VTE)	BMI ≥ 30	
	 Noted on self-respondent survey (defined as blood clot requiring anticoagulation treatment) 	Age > 35 years PMHx for thrombophilia Arterial/venous lines or ports Pmhx cancer Smoking	
	Liver outcomes	BMI	Obesity contributes to
	 Liver disease, non-cirrhosis Gallstone, requiring surgery/procedure (defined as present or absent as 	Comorbidity with diabetes	liver dysfunction Associated with worse disease (reduced immunity)
	recorded in CFFPR)	Hepatitis	Risk factor for liver dysfunction
		CF genotype class Length of hormonal contraceptive use (person-year of exposure)	
	 Serum ALT, GGT (meets criteria if hepatic transaminases and GGT levels exceed upper limit of normal on at least 3 consecutive occasions over 12-month period) (12) 		Will track meeting criteria annually over time
	CF-related diabetes		
	 Serum ogtt trends New onset insulin resistance or diabetes (defined as 		

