8.0. Methods: Assignment of interventions

8.1. Allocation

Participants will belong to a group based on their choice of contraception. Women with CF will be allocated to hormonal group (intervention), non-hormonal groups (control), and never used contraception.

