9.1.3. Patient Surveys

Table 10: Information in online, self-respondent surveys

Survey O	nce Enrolled
• Demog	graphics: marital status, race/ethnicity, and education
	nedical history: ever smoked, ever had a blood clot requiring anticoagulation, # PICC lines placed, PORT in (dates)
Medic	ation history: ever taken CFTR modulator (with start and stop dates)
-	al history: Tubal ligation, hysteroscopic sterilization, hysterectomy, bilateral oophorectomy, other operation as made it impossible to get pregnant
• Menst	rual history: menarche, regularity of menstruation, menopause
• Contra	aception questionnaire
•	Questions regarding types of contraception used since 2008, start and stop dates of each method or age at first/last use. Questions are based off of the National Survey of Family Growth (NSFG)
• Pregna	ancy history questionnaire

- - Includes number of pregnancies in lifetime, year(s) pregnant, outcome of pregnancy, whether pregnancy was planned or not
 - Additional questions to include for funded study ([name] and [name]): times visited CF center during pregnancy and type of provider who cared for participant during pregnancy, ART

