9.3. Statistical Methods

Because this is a retrospective cohort study, we are most interested in determining whether this exposure (to hormonal contraception) is associated with our primary outcome (counting the number of pulmonary exacerbations requiring additional IV in a given year) and/or our secondary outcomes (new respiratory microbiology, liver disease/non-cirrhosis, gallstone, requiring surgery/procedure, improved BMI, incidence of VTE, osteoporosis and fragile bone fracture). Women on hormonal contraception will be compared to the primary control group of women on non-hormonal contraception. We will also compare to women on no contraception, as the secondary control group. We will exclude persons with these existing diagnosis at the start of the follow up period for outcome data (January 1, 2010). Within this objective we will be able to calculate incidence rates, relative risks and confidence intervals. We will use Poisson regression to calculate progestin-only and combined hormonal method to non-hormonal method pulmonary exacerbation rate ratios and 95% confidence intervals. This allows for adjustment of follow-up time of each individual.

(Objective 1a): We will evaluate lab values over time (ppFEV1%, serum AST, ALT, alkaline phosphatase) to determine if trends between hormonal contraceptive users and non-hormonal contraceptive users differ. See Table 5 for confounders and covariates that we will use to adjust for the primary and secondary outcomes.

We will model ppFEV1 via generalized estimating equations (GEE), allowing for correlation within a subject, and compare via a fixed effect for exposure. Among women who change or stop contraception, we will estimate and compare within-participant difference in outcomes via the model (if numbers allow). We will censor women who switch method types or become pregnant, and for 6 months post pregnancy, for the primary analysis and subsequently follow them to leverage within-patient data and analyze changes in pulmonary status and contraception. Presence of respiratory microbiology will be estimated longitudinally via GEE with a logit link function. Graphic displays and summary statistics will be used; all *p* values will be two-sided.

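### The primary-analysis censoring rule omits stopping, so time after a woman stops hormonal contraception can be left in the hormonal group

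*Combined protocol and SAP*

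**What the plan says.** Section 9.3 sets one censoring rule: "We will censor women who switch method types or become pregnant, and for 6 months post pregnancy, for the primary analysis". Two events are named, a change of method type and pregnancy. The sentence just before it treats stopping as a separate event and gives it a different, conditional analysis: "Among women who change or stop contraception, we will estimate and compare within-participant difference in outcomes via the model (if numbers allow").

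The group definitions come in two forms:

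- Section 8.1 assigns women, not person-time: "Women with CF will be allocated to hormonal group (intervention), non-hormonal groups (control), and never used contraception".
- Section 9.3 uses present-tense wording for the primary contrast, "Women on hormonal contraception will be compared to the primary control group of women on non-hormonal contraception", and for the secondary one, "We will also compare to women on no contraception, as the secondary control group".

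On exposure data, Table 10 in section 9.1.3 lists "Questions regarding types of contraception used since 2008, start and stop dates of each method or age at first/last use". Table 5 in section 7.5 has "Length of hormonal contraceptive use (person-year of exposure") among the covariates; it is not given there as a rule for dividing time at risk.

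The Poisson model adjusts for each woman's follow-up time. Outcome follow-up starts on 1 January 2010 (section 9.3) and runs to 2018 or 2019 (section 5.0).

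**The concern.** Take a woman who used a pill from 2011 to 2013 and nothing since. She has not moved to another method type, she is not pregnant, and she is not a never-user. Neither censoring event applies to her, and the third group in 8.1 is closed to her. Applied as written, the two rules leave her exacerbations from 2014 onward in the hormonal group, while she takes no hormones. A woman who stops in order to conceive is in the same position until conception.

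Unexposed time in the exposed group would normally pull a protective rate ratio toward 1 and cost power on the primary endpoint. It could also credit hormonal use with safety events that occur long after stopping. Because the data are retrospective, the choice may otherwise be made after the registry outcomes are in hand.

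**Working it through.** **1. Does any text assign post-stop time?** The censoring sentence in 9.3 does not mention it. The sentence before it offers only a within-woman comparison, and only if numbers permit. Section 8.1 has no group for a past user. Table 5 uses duration as a covariate. No section says that post-stop time is removed, moved or kept.

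**2. The plan's own power figure.** Inputs from section 7.7: 0.8 exacerbations per year, rate ratio 0.70, alpha 0.05, about half of the women on hormonal methods, 575 enrolled, 15% attrition. Section 9.3 makes tests two-sided. Analysable N = 575 × 0.85 = 489.

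Power = Φ(|ln RR| / √(φ(1/E0 + 1/E1)) − 1.96), with E0 and E1 the expected events in the control and hormonal groups, one year per woman, and φ the overdispersion.

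- E0 = 244.5 × 0.8 = 195.6; E1 = 195.6 × 0.70 = 136.9.
- φ = 1: 0.357/0.1114 − 1.96 = 1.24, so power is 0.89. The text states 80%, and Table 8 interpolates to about 0.81 at 489. The stated inputs alone do not reproduce it.
- φ = 1.3: 0.357/0.1270 − 1.96 = 0.85, so power is 0.80. This value gives 0.768, 0.790, 0.810, 0.829, 0.846 and 0.861 for N = 450 to 575, within about 0.01 of every row of Table 8.

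The value φ = 1.3 is an assumption chosen to match the table. The mismatch is a separate matter and does not bear on the censoring rule. I take 0.70 as hormonal to non-hormonal, as Table 8 does; the text of 7.7 attaches it to progestin-only against combined.

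**3. Effect of keeping post-stop time as exposed.** Let f be the share of hormonal-group person-time that falls after stopping. Assume a true on-method ratio of 0.70, a post-stop rate equal to the control rate, no carry-over, and stopping unrelated to health.

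- Expected ratio = 0.70(1 − f) + f = 0.70 + 0.30f.
- Share of the log ratio lost = 1 − ln(expected ratio)/ln(0.70).
- If time is kept, power uses the diluted ratio and E1 = 195.6 × (0.70 + 0.30f).
- If time is censored at stopping, the ratio stays 0.70 and E1 = 136.9(1 − f).

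With N = 489 and φ = 1.3:

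| f | Expected ratio | Log ratio lost | Power, time kept | Power, censored at stop |
|---|---|---|---|---|
| 0.10 | 0.73 | 12% | 0.71 | 0.78 |
| 0.20 | 0.76 | 23% | 0.60 | 0.75 |
| 0.30 | 0.79 | 34% | 0.48 | 0.71 |
| 0.40 | 0.82 | 44% | 0.37 | 0.66 |

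With φ = 1 the pairs are 0.82/0.87, 0.71/0.85, 0.59/0.82 and 0.46/0.77.

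The last column takes no time from the controls. If they lose the same share, power = Φ(2.807√(1 − f) − 1.96) = 0.76, 0.71, 0.65 and 0.58 at φ = 1.3, still above the kept-time column at each f.

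**4. How large might f be?** The documents do not say. As an illustration only, suppose that all hormonal users are on the method at the start, that 10% stop each year, and that the window is nine years. With h = −ln(0.9) = 0.105, f = 1 − (1 − e^(−9h))/(9h) = 0.35, and the expected ratio is about 0.81. At 5% a year, f = 0.20 and the ratio is 0.76.

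**The case against.** A reader might infer that the plan directs post-stop time to be counted as hormonal. It does not; it is silent. The present-tense group wording in 9.3, the survey's start and stop dates and the person-years of exposure in Table 5 all fit a current-use analysis. The censoring sentence goes on to follow the censored women for changes in contraception, right after the sentence on women who change or stop, so its authors may have meant switching to include moving to no method. It also sits in the ppFEV1 paragraph, and reaches the Poisson model only through its reference to the primary analysis. The never-user label in 8.1 may be loose: 4.1 and 9.3 describe non-users, and 7.2 defines the population by having used some method.

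This stands as a reason not to call retention a stated rule. It does not close the gap: the current-use reading conflicts with 8.1, and if the censoring sentence does not reach the Poisson model, that model has no rule for ending exposure.

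A reader might also infer that bias toward 1 is certain. It is not. If women stop because of illness, or stop to conceive while well, it could go either way. Nor does a condom user who stops dilute the ratio: under the same assumption, her later time still carries the control rate. And the window from 2010 is a calendar maximum, not each woman's follow-up; women can enrol at 18.

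**Conclusion.** The concern holds as an omission in a stated rule. Applied literally, 9.3 and 8.1 allow post-stop time to remain in the hormonal group, and nothing elsewhere removes it; a current-use reading is also open, so two competent analysts could report different primary rate ratios. If the time is kept, the ratio would probably move toward 1: from 0.70 to between 0.73 and 0.82 for f of 10% to 40%, a loss of 12% to 44% of the log ratio. That range rests on an assumed f, a post-stop rate equal to the control rate, no carry-over and stopping unrelated to health. The documents support none of these directly, and health-related stopping could alter the size or the sign. They do not support the stronger claims that the plan instructs retention or that dilution is certain.

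**What to change.** Amend 9.3 along these lines:

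> For the primary Poisson analysis and the ppFEV1 model, a woman's time in a contraceptive group ends at the earliest of stopping the method, switching method type, or pregnancy. Later time with no method in use counts only in the secondary no-contraception comparison. Standard errors are clustered by woman.

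Clustering is needed because one woman may then contribute to two groups, and 9.3 states no within-woman correlation for the Poisson model. The existing six-month exclusion after pregnancy can stay as it is.

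Also:

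- reconcile the never-user group in 8.1 with the no-contraception group in 9.3;
- state how a stop is dated when the survey yields only age at last use, since Table 10 accepts "start and stop dates of each method or age at first/last use";
- settle the rule before registry data are linked.

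No new data collection is needed: the survey asks about stopping, and the Appendix requests care-episode start dates, so exacerbations can be placed before or after a stop. The cost is episode-level coding, less person-time in the hormonal and non-hormonal groups, and some coarse stop dates. On the assumptions above, power is still higher than with the time left in at every f examined.

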10.0. Methods: Monitoring

10.1. Disposition

The study ends for the participants once participants complete the survey and the CF center research staff complete the case report forms.

10.2. Safety Assessment Methods

Because this is an observational study, we do not anticipate any adverse events on account of this study. Participants may feel uncomfortable answering questions about their medical history, birth control and pregnancy history. They may decline to answer any of the online survey questions at any time. Participants may feel uncomfortable with the research team accessing their data from CFFPR. The research team will do their best to protect your privacy during this process.

10.3. Adverse Event Management and Reporting

An adverse event for this study may include a breach of confidentiality. Should a confidentiality breach occur, it will be reported to the Institutional Review Board by the investigator (according to the local policies). No Data Safety Monitoring Board will be used for this study.

Participants will also be provided the site PI and study PIs contact information should a participant believe they have a medical problem or illness related to this research. The principal investigators at each site will be responsible for monitoring participant confidentiality.

10.4. Duration of Project (see Table 11)

- The duration of the project is expected to be about 36 months.
- Recruitment is expected to take 12 months.
- Merging of the data and cleaning the database is expected to take up to 4 months.
- Data analysis will take 3 months.
- Creation of the web-based REDCap database for data entry will occur before enrollment begins, and data entry will be ongoing throughout the study.

11.0. Ethics and Dissemination Plan

All of the information participants and clinics provide for this study will be kept confidential. When participants open the online survey, they will automatically be assigned a subject ID number. Based on the assigned ID number, centers will be able to identify which of their patients have already enrolled in the study. This number will be connected to the identifying information provided by participants to locate their records in the CFFPR. After participants complete their online survey, UW will send the identifying information (CFFPR ID or name, date of birth, and zip code) along with the subject ID number assigned by UW to the CFFPR team. They will use this information to pull participant data from 2010-year as recent as possible. They will provide us with this data attached to the subject ID number. The link between participant identifiers and the research data will be destroyed after the records retention period required by state and/or federal law.

Government or university staff sometimes review studies such as this one to make sure they are being done safely and legally. If a review of this study takes place, participant records may be examined. The reviewers will protect the subjects' privacy. The study records will not be used to put participants at legal risk of harm.

We plan to present our data at the North American CF Conference and the Society of Family Planning Conference. We will develop a summary paper from this feasibility study consistent with "Strengthening the Reporting of Observational Studies in Epidemiology" (STROBE) guidelines for reporting observational studies for publication (14).

Table 11: Project Timeline

	Pre- Award Period	YEAR 1							YEAR 2					
Activities & Timeline		2019			2020						2021			
Activities & filmeline		Aug - Sep	Oct - Nov	Dec	Jan- Feb	Mar - Apr	May - Jun	Jul	Aug - Oct	Nov - Dec	Jan - Feb	Mar - Apr	May - Jun	Jul
IRB application submission and approval														
Institutional subcontract finalization														
Interdisciplinary Team meetings (Zoom for remote participants)														
Progress report due to CFF (due 90 days before start of next award period)							Due 5/1/20						Due 5/1/21	
Financial report due to CFF (due 90 days after completion of prior award period)										Due 11/1/20				
CFFPR Data Application submission and approval														
CFF Confidentiality Agreement and Information Use Agreement														

 - Race includes 'Some other race'
 - Patient is Hispanic
- Health insurance
 - Health insurance policy (i.e. private insurance)
 - Medicare
 - o Medicaid
 - State special needs program (BCMH, CCS, CRS, GHPP...)
 - TriCare or other military health plan
 - o Indian Health Service
 - Other health insurance
 - o Patient has no health insurance for the entire year
 - Patient covered on their parents' insurance plan
 - o Receives free medicine/assistance from patient assistance program
- Socioeconomic characteristics
 - Patient's education
- Smoking
 - Patient smokes cigarettes during the reporting year
- Research involvement
 - o Patient participated in interventional (drug) studies
- Patient pregnancy
 - o Patient was pregnant during the reporting year
 - Outcome of patient's pregnancy

II. DIAGNOSIS

- Diagnosis date
 - First year in the CFF Patient Registry
 - Research involvement
 - Patient participated in interventional (drug) studies
- Genotyping
 - \circ $\;$ Has this patient been genotyped
 - Mutation classification
 - Name of the first mutation
 - Mutation 1 Class
 - Name of the second mutation
 - o Mutation 2 Class
 - o Delta F508

III. CLINIC VISITS

• Visit details

- Date of Encounter [PHI]
- Encounter age [PHI]
- Pulmonary exacerbation encounter level
 - Assessment of potential pulmonary exacerbation
- Pulmonary exacerbation summarized by calendar year
 - o Any pulmonary exacerbation assessment in the year
 - Any pulmonary exacerbation assessment positive in the year
 - # encounters with pulmonary exacerbation assessments: absent
 - o # encounters with pulmonary exacerbation assessments: mild exacerbations
 - o # encounters with pulmonary exacerbation assessments: moderate exacerbations
 - # encounters with pulmonary exacerbation assessments: severe exacerbations
 - Encounter exacerbation treatment: Incr. airway clearance
 - Encounter exacerbation treatment: Oral NON-quinolone antibiotic
 - Encounter exacerbation treatment: Oral quinolone antibiotic
 - Encounter exacerbation treatment: Inhaled Antibiotic
 - o Encounter exacerbation treatment: Inhaled + Oral NON-quinolone antibiotic
 - Encounter exacerbation treatment: Inhaled + oral quinolone antibiotic
 - Encounter exacerbation treatment: None of the above

IV. CLINICAL MEASUREMENTS

- Anthropometric measures encounter level
 - Patient's height
 - BMI Value
 - BMI Percentile
 - Weight of Patient
- Pulmonary function tests encounter level
 - Measure of FVC
 - Percent predicted relative to predicted FVC
 - Predicted Value for FVC using GLI reference equations
 - Measure of FEV1
 - Percent predicted relative to predicted FEV1
 - Predicted Value for FEV1 using GLI reference equations
- Lab values encounter level
 - Alanine Aminotransferase (ALT or SGPT), IU/L
 - Fecal elastase value (microg/g of stool)
 - Alkaline phosphatase 2 hour blood glucose (mg/dL)
 - Total bilirubin, mg/dL
 - Hgb A1C value, %
 - o Liver enzymes drawn (pre-2010) Aspartate aminotransferase
 - o GGTP (gamma glutamyl transpeptidase), IU/L
 - Fasting glucose level (mg/dL)
 - OGTT Fasting glucose level (mg/dL)
 - Lab values summarized by calendar year
 - Fasting glucose level (mg/dL)
 - OGTT fasting glucose level (mg/dL)
 - 2-hour blood glucose (mg/dL)
- Screening tests
 - Liver function tests performed
 - o DEXA scan for bone density performed in the reporting year
 - DEXA scan result is normal

- DEXA scan result is osteopenia
- DEXA scan result is osteoporosis
- DEXA scan result is other
- DEXA scan result is unknown

V. MICROBIOLOGY

- Bacteria encounter level
 - Was bacterial culture done?
 - Date of bacterial culture [PHI]
 - Culture results
 - Staphylococcus aureus
 - o MRSA
 - o Any Burkholderia Complex species
 - Multidrug-Resistant P. aeruginosa (MDR-PA) Infection
 - Stenotrophomonas
 - o MSSA
 - Pseudomonas aeruginosa found in the culture
 - Mucoid Pseudomonas aeruginosa
 - Non-mucoid Pseudomonas aeruginosa
 - Mucoid Pseudomonas aeruginosa status unknown
- Mycobacteria encounter level
 - Was mycobacterial culture done?
 - Date of myco culture [PHI]
 - o Myco culture results
 - Mycobacterial tuberculosis
 - Mycobacterium terrae
 - Mycobacterium other
 - Mycobacterium abscessus/chelonae
 - Mycobacterium avium complex
 - Mycobacterium fortuitum group
 - o Mycobacterium gordonae
 - Mycobacterium kansasii

VI. TREATMENTS

•

- Antibiotics encounter level
 - o Chronic oral macrolide antibiotic
 - o Azithromycin
 - o Clarithromycin
 - o Sulfa
 - o Amoxicillin
 - o Tetracycline
 - o Other oral antibiotic
 - o Other chronic oral antibiotic
 - o Quinolone
 - Cephalosporin
- CFTR modulators encounter level
 - On Ivacaftor medication (VX-770)
 - VX770 (Ivacaftor) dosage
 - Ivacaftor/Lumacaftor (i.e., Orkambi)
 - Ivacaftor/Lumacaftor (i.e., Orkambi) dosage
- Other treatments encounter level

- Patient is taking enzymes
- CF-specific vitamins (i.e. vitamins A, D, E and K)
- o **Exercise**
- Other treatments annual
 - Was the patient started on treatment for NTM

VII. COMPLICATIONS

- CF related diabetes encounter level
 - o CFRD Status
 - Chronic renal insufficiency
 - Chronic renal failure requiring dialysis
- Liver disease encounter level
 - o Gall stones
 - Gall stones, requiring surgery/procedure
 - Liver disease, cirrhosis
 - Acute hepatitis
 - Acute hepatitis infectious
 - Acute hepatitis non-infectious
 - Acute hepatitis unknown
 - Liver disease, non-cirrhosis
 - Hepatic Steatosis
 - Liver disease, other Acute liver failure
 - Other complications encounter level
 - Bone fracture
 - o Osteopenia
 - Osteoporosis
 - Cancer confirmed by histology

VIII. CARE EPISODES (HOSPITALIZATIONS/HOME IV)

- Care episodes
 - Start date for care episode [PHI]
 - End date for care episode [PHI]
 - # home IV nights with reason pulmonary exacerbation
 - # hospitalization nights with reason pulmonary exacerbation
- Care episodes summarized by calendar year
 - Total # pulmonary exacerbations treated by IV antibiotics
 - # nights in hospital for pulmonary exacerbations
 - # nights on home IV for pulmonary exacerbations
 - o Total # pulmonary exacerbation treated by IV antibiotics (incl unknown)
 - # nights hospital for pulmonary exacerbation (incl unknown)
 - o # nights home IV for pulmonary exacerbation (incl unknown)
